**METHODS:** The study is a randomized clinical trial with repeated measurements. A convenient sample of 72 adults who were treated with anticoagulants for atrial fibrillation was recruited from two teaching hospitals in northern Taiwan. Participants were randomly assigned 1:1 to either the control group (n = 36) or the intervention group (n = 36) after completion of baseline questionnaires. Allocation was balanced by site by using a minimization method. The health belief model based self-management intervention comprised two main components: a 60-minute individual face-to-face instruction and six follow-up telephone calls. Participants in the control group received regular medication education, 10-minute individual instruction for health knowledge and six follow-up telephone calls for concerning health. Data were collected at baseline, third month, and sixth month in both groups, by using self-administered questionnaires. The investigator administered the study questionnaire after obtaining informed consent from each subject. The data collection took place at the waiting areas outside the outpatient clinics during the patients' visits to the clinics. For subjects who were unable to read the questionnaire due to vision or other problems, the investigator read each question to help them complete the questionnaire. The instruments include the Atrial Fibrillation Knowledge Scale, Satisfaction Scale about Service and Warfarin Treatment, Belief about Anticoagulation Survey, and Self-Efficacy for Appropriate Medication Use Scale.

**DATA ANALYSIS:** Data were analyzed using the Statistical Package for Social Sciences 20.0 (SPSS, Inc., Chicago, IL, USA). Descriptive analyses were used to describe study variables. Independent t-tests and one-way analysis of variance (ANOVA) were performed to analyze the baseline equivalent between study groups. The generalized estimating equations were used to analyze the efficacy of the intervention for enhancing knowledge, knowledge, perceived benefits, perceived barriers, self-efficacy, and adherence to anticoagulant therapies in patients treated with oral anticoagulants for atrial fibrillation.

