## Participant Flow Template

Recruitment Details	Patients with AFib were recruited from the cardiology clinics of two general hospitals in northern Taiwan. Potential participants were referred by cardiologists and screened by one of the investigators to determine their eligibility
[*] Pre-assignment Details	

Period ①		①		
*	Overall Study	EG	CG	
	*	Intervention Group	Control Group	
	*§ Arm/Group	Number of Participants ④	Number of Participants ④	Number of Participants
	* Started	36	36	
	[*] Milestone			
	[*] Milestone			
	[*] Milestone			
	* Completed	33	30	
	Not Completed	(automatically calculated)		
	Reason Not Completed Type ③			
	[*] Adverse Event			
	[*] Death			
	[*] Lack of Efficacy			
	[*] Lost to			
	[*] Physician			
	[*] Pregnancy			
	[*] Protocol			
	[*] Withdrawal by	1	2	
	[*] Other Change Medication	1	2	
	[*] Other Operation	1	0	

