## Outcome Measure Template

	Primary	Secondary	Other Pre-specified	Post-Hoc
* Outcome Measure	(Select One)			
* Outcome Measure	Anticoagulant medication adherence			
* Outcome Measure	Participants were monitor for up to 24 weeks, These is the score of participants who had been monitor for medication adherence. The study adapted Adherence to Refills Medications Scale (ARMS) assess the participants' medication adherence when taking anticoagulants			
Description	Ups to 24 weeks			
* Outcome Measure Time	Ups to 24 weeks			

More details available in the Results Data Element Definitions. April 2017

* Measure Type (Select One)	* Measure of (Select One)	EG		CG			
* Row/Category Title	* Row/Category Title						
* § Arm/Group Description		Intervention group		Control group			
* Number of Participants Analyzed	[*] Analysis: Population	36		36			
All participants with baseline and at least fellow up for 24 weeks							
Count of Participants ③	Not Applicable ④						
Mean	Standard deviation						
Median	Standard Error						
Least Squares Mean	Inter-Quartile Range						
[*] Row/Category Title	Medication adherence	8.1	1.4	9.2	2.2		③ ④
[*] Row/Category Title			③ ④		③ ④		③ ④
* Unit of	score						

*Statistical Analysis Template*

Statistical Analysis Overview	* Comparison Group Selection ①	 ✓ Arm/Group 1	 ✓ Arm/Group 2	 Arm/Group 3
	Comments ②			
	* Type of Statistical Test	(Select One) Superiority Non-inferiority Equivalence Other (for example, single group or other descriptive analysis)		
	[*] Comments ③			
Statistical Test of Hypothesis	[*] P-Value (if applicable)	0.05 [calculated value, not the a priori threshold for statistical significance]		
	Comments ②			
	[*] Method (required if p-value entered)	(Select One) ANCOVA ANOVA Chi-Squared Chi-Squared, Corrected Cochran-Mantel-Haenszel	Fisher Exact Kruskal-Wallis Log Rank Mantel-Haenszel McNemar	Mixed Models Analysis Regression, Cox Regression, Linear Regression, Logistic Sign Test t-Test, 1-Sided F-Test, 2-Sided Wilcoxon (Mann-Whitney) Other ( )
	Comments ②			

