Method of Estimation	[*] Estimation Parameter (if applicable)	(Select One) Cox Proportional Hazard Hazard Ratio (HR) Hazard Ratio, Log	Mean Difference (Net) Median Difference (Final Values) Median Difference (Net) (generalized estimating equation) Odds Ratio (OR)	Odds Ratio, Log Risk Difference (RD) Risk Ratio (RR) Risk Ratio, Log
	Estimated Value	0.5 (calculated value)		
	Confidence Interval (if applicable)	Level: 95 % Confidence Interval	Number of Sides: (Select One) 2-sided	1-sided
	Parameter Dispersion	Lower Limit: _____	Upper Limit: _____	Type: (Select One) Standard Deviation Standard Error of the Mean
	Estimation Comments ②			
Other Statistical Analysis ④	A generalized estimating equation (GEE) 28 was used to model each outcome variable as a function of group effect, time effect, and group by time interaction effect.			

\* Required [\*] Conditionally required

- ① Use the checkboxes to select the Arms/Groups (pre-populated from the Outcome Measure) involved in the statistical analysis.
- ② (Optional) Include any relevant information about the row above (e.g., the null hypothesis, details of the power calculation, adjustment for multiple comparisons, the *a priori* threshold for statistical significance, the direction of the comparison). Do not include written results or conclusions.
- ③ If a non-inferiority or equivalence analysis, information on the definition of the non-inferiority or equivalence margin is required.
- ④ If the statistical analysis cannot be submitted using the Statistical Test of Hypothesis or Method of Estimation options, provide a description and the results

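### As written, the adherence analysis set is a 24-week completer rule that the GEE does not need and that contradicts the 36/36 printed beside it

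*Combined protocol and SAP*

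**What the plan says.** The only analysis-population rule in the document stands in the Outcome Measure Template, against the adherence outcome: "All participants with baseline and at least fellow up for 24 weeks". The number analysed in the same table is "Analysis: Population 36 36", that is, 36 per arm.

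The Study Protocol (Methods) states that "Participants were randomly assigned 1:1 to either the control group (n = 36) or the intervention group (n = 36"). The Participant Flow Template then gives "Completed 33 30" for intervention and control.

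On timing, the Methods say "Data were collected at baseline, third month, and sixth month in both groups". On the model, the Statistical Analysis Template says that a GEE "was used to model each outcome variable as a function of group effect, time effect, and group by time interaction effect".

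There is no intention-to-treat statement, no missing-data method, no stated working correlation, and no rule on whether a non-completer's month-3 score enters the model.

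**The concern.** Whether a participant reaches 24 weeks is known only after randomisation. A set defined by it compares those who stayed, not those who were assigned, and can be biased if staying is related to earlier adherence.

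The restriction also buys nothing. A GEE on baseline, month 3 and month 6 can use a participant who has only the first two, so requiring 24 weeks can only discard usable scores.

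The adherence result is exposed because non-completion is 3 of 36 in one arm and 6 of 36 in the other, and because some listed reasons could bear on adherence: "Other Change Medication 1 2" and "Withdrawal by 1 2". Correcting only the printed count to match the sentence would leave a completer analysis as the main analysis.

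**Working it through.** **1. Does the rule reproduce the printed count?**

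Inputs: 36 and 36 started, 33 and 30 completed (Participant Flow Template); 36 and 36 analysed (Outcome Measure Template).

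| | Intervention | Control | Total |
|---|---|---|---|
| Randomised and started | 36 | 36 | 72 |
| Completed (rule read literally) | 33 | 30 | 63 |
| Excluded by the rule | 3 (8.3%) | 6 (16.7%) | 9 (12.5%) |
| Printed as analysed | 36 | 36 | 72 |

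It does not. The printed count equals everyone randomised. The listed reasons sum to 1 + 1 + 1 = 3 in the intervention arm, which matches, but to 2 + 2 + 0 = 4 in the control arm against 6, so two control non-completers have no listed reason.

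**2. Do the printed results show which set was used?**

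Take the printed 8.1 (1.4) and 9.2 (2.2) as mean (SD); the selected dispersion type is not legible. The difference is 8.1 - 9.2 = -1.1.

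- At 36/36: SE = sqrt(1.4²/36 + 2.2²/36) = 0.43, p = 0.014.
- At 33/30: SE = sqrt(1.4²/33 + 2.2²/30) = 0.47, p = 0.020 pooled, 0.023 Welch.

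The table enters a p-value of 0.05 and an estimate of 0.5. Neither denominator gives these, so they do not identify the set.

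**3. Precision at month 3, if all 9 gave a month-3 score.**

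With a common SD, the SE ratio is sqrt(1/33 + 1/30) / sqrt(1/36 + 1/36) = 0.2523 / 0.2357 = 1.070, about 7%. With the printed SDs it is 0.4698 / 0.4346 = 1.081, about 8%.

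**4. Bias in the stated contrast, if dropout depends on the month-3 score.**

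Assumptions, none of them in the documents: visit correlation 0.5 between every pair of visits; true difference -1.1; all dropout after month 3, at 3/36 and 6/36; odds of dropout multiplied by 2 to 4 per SD of month-3 score. The SDs are the printed 1.4 and 2.2. The contrast is the group-by-time one, change from baseline.

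| Analysis | Month-3 bias | Month-6 bias |
|---|---|---|
| Completers only | about 0.09 to 0.13 | about zero |
| All randomised, all scores, exchangeable correlation | about 0.01 or less | about 0.01 or less |
| All randomised, all scores, independence | about 0.01 | about 0.09 to 0.14 |

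These are simulated values, with a Monte Carlo error of roughly 0.007 in 4,000 runs.

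A direct calculation confirms them. For odds ratios 2, 3 and 4, integrating the logistic dropout rule over a normal score lowers the completers' mean month-3 score by 0.08, 0.12 and 0.14 points in the intervention arm and by 0.24, 0.35 and 0.40 in control. The between-arm difference in these shifts is 0.16, 0.23 and 0.27 (before rounding of the parts).

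- *Completers, month 3.* The completers' baseline mean moves by 0.5 times the month-3 shift, so the change contrast is off by (1 - 0.5) times the difference: 0.08, 0.12 and 0.13.
- *Completers, month 6.* Baseline and month-6 means both move by 0.5 times the shift, so the change contrast is off by zero. This cancellation rests on the assumed equal correlations.
- *Independence, month 6.* Selected month-6 scores are set against unselected baselines, so the error is 0.5 times the difference: 0.08 to 0.13.

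The bias is positive, so it pulls -1.1 towards zero: at month 3 by 0.09/1.1 = 8% to 0.13/1.1 = 12%. If dropout is unrelated to score, every row is unbiased and only the precision in step 3 is at issue.

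**The case against.** A reader might infer that nine participants were in fact dropped and the as-randomised comparison given up. The documents do not support that: the same table prints 36 and 36 analysed, and on that count nobody is excluded.

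The sentence is also garbled. It may have meant at least one follow-up within 24 weeks, and the time frame beside it runs up to 24 weeks. Nor does any text say that the sentence decides which visits enter the GEE; it annotates a row with one score per arm. Both points stand. Yet even the milder reading is a condition met after randomisation, and under any reading the sentence needs rewriting.

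A reader might also infer that month-3 scores have been thrown away. Dropout timing is not given, so it is unknown whether any non-completer had one.

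Nor can one say that the arms truly differ in dropout: 33/36 against 30/36 has Fisher p = 0.48, and no link between leaving and adherence is documented.

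The strongest technical objection is that the completer rule does no measurable harm at month 6 under the assumptions used, while an all-available GEE with independence correlation would do some. That stands, and it is why the remedy must name the working correlation as well as the population.

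**Conclusion.** The concern holds for the rule as written. Applied to the trial's own flow figures, the sentence would exclude 9 of 72 participants, 3 against 6, from a model that has no need to exclude them. It contradicts the 36/36 printed in the same table, and the documents do not say which governs.

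If the sentence governs, the cost at month 3 is a standard error about 7% too wide, provided all nine gave scores then. If dropout is also score-related as assumed, there is a bias of about 0.09 to 0.13 points on a difference of 1.1. At month 6 the bias is about zero. If the count governs, nothing was lost and only the sentence is wrong.

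The dropout odds ratios, the visit correlation, the true difference and the timing of dropout are assumptions. This is a modest point that should be put right, not evidence that the reported result is biased.

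**What to change.** Replace the population sentence with:

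> All 72 randomised participants, analysed in the arm assigned; every available baseline, month-3 and month-6 score enters the GEE whether or not the participant reached 24 weeks.

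With it:

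- specify an exchangeable or unstructured working correlation, not independence;
- report by arm how many participants have no post-baseline score, and account for the two control non-completers without a listed reason;
- make the number analysed agree with this set;
- keep the 24-week completer set as a sensitivity analysis only.

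The cost is one sentence, one stated model option and one re-run on data already collected, with no new participants or visits. If all 72 were already analysed in this way, the sponsor need only correct the sentence and confirm it.

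### Non-completion was 3 of 36 v 6 of 36, yet the GEE has no stated missing-data method or sensitivity analysis and its population is tied to 24-week follow-up; bias is an open risk, and modest differences in those who left could cost nominal significance.

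*Combined protocol and SAP*

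**What the plan says.** The METHODS paragraph of the Study Protocol sets arms of equal size ("control group (n = 36) or the intervention group (n = 36"), with questionnaires at baseline, month 3 and month 6. Randomisation follows the baseline questionnaires. Under DATA ANALYSIS, "The generalized estimating equations were used to analyze the efficacy of the intervention". The Other Statistical Analysis row of the results form adds that the GEE "was used to model each outcome variable as a function of group effect, time effect, and group by time interaction effect".

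The Participant Flow Template records "Completed 33 30" (intervention, then control). Its listed reasons are "Withdrawal by 1 2", "Other Change Medication 1 2" and "Other Operation 1 0".

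The Outcome Measure Template reports "Medication adherence 8.1 1.4 9.2 2.2". It limits the analysis population to people with a baseline measurement and 24 weeks of follow-up, yet prints 36 and 36 as the numbers analysed. The accompanying form enters a p-value of 0.05, in a field meant for the calculated value, and an estimate of 0.5 without confidence limits. It also boxes a two-sided F-test, which does nothing about missing visits.

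Nowhere do the documents give a working correlation, weighting, imputation, an assumption about missing data, or a sensitivity analysis.

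**The concern.** Leaving the study because of withdrawal or a change of medication could plausibly be linked to adherence to the anticoagulant or to beliefs about it, and these are the outcomes. If people left according to how they were scoring, the month-6 comparison sets differently selected groups side by side. A GEE without weights or imputation does not in general correct for that. Whether it comes close depends on two things the documents leave open: whether the dropouts' earlier visits enter the model, and which working correlation is used.

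The population entry makes this sharper. If only people with 24 weeks of follow-up are analysed, and their visits are complete, a model with group, time and group-by-time simply reproduces the observed group means at each visit, whatever common working correlation is chosen. The dropouts' earlier scores then contribute nothing. At stake are the adherence result and every mediator result analysed in the same way.

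**Working it through.** **1. Non-completion (Participant Flow Template).**
- Intervention: 36 − 33 = 3, and 3/36 = 8.3%. Control: 36 − 30 = 6, and 6/36 = 16.7%.
- Difference: 8.3 percentage points, 95% CI 0.083 ± 1.96 × √[(6/36)(30/36)/36 + (3/36)(33/36)/36] = 0.083 ± 0.152, or about −6.8 to 23.5 points. Fisher exact p = 0.48.
- Listed reasons: 1 + 1 + 1 = 3 in intervention and 2 + 2 + 0 = 4 in control. So 6 − 4 = 2 control dropouts have no listed reason.

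**2. The form's own figures.** The dispersion label is not marked, so I take the second number of each pair as an SD. A two-sample comparison of 8.1 (1.4) with 9.2 (2.2) gives p = 0.011 to 0.014 with n = 36/36 and p = 0.019 to 0.023 with n = 33/30 (Welch t, pooled t and normal variants). None gives the entered 0.05. The mean difference is 1.1, not 0.5. The 0.5 could be a GEE coefficient, which cannot be checked without baseline means.

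**3. How far dropouts must differ.** Assume month-6 means (SDs) of 33 and 30 completers.
- SE = √(1.4²/33 + 2.2²/30) = 0.470. Welch df = 48.3, critical t = 2.010, half-width 0.944.
- Difference (intervention − control) = −1.1, 95% CI −2.04 to −0.16. The margin before the interval reaches zero is 0.1555.
- Suppose dropouts lie d points from their own arm's completers. The size of the all-randomised difference becomes 1.1 − d(3/36 + 6/36) = 1.1 − 0.25d if the arms shift in opposite, gap-narrowing directions. It becomes 1.1 − d(6/36) if only control dropouts shift, and 1.1 − d(6/36 − 3/36) if both shift downwards.
- Welch t: 0.1555/0.25 = 0.62; 0.1555/(6/36) = 0.93; 0.1555/(3/36) = 1.87.

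Shift at which the 95% interval reaches zero, across the test variants, with the SE held fixed:

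| Pattern of shift | SE from n = 33/30 | SE from n = 36/36 | Shift for zero difference |
|---|---|---|---|
| Opposite, gap-narrowing | 0.62 to 0.79 | 0.92 to 0.99 | 1.1/0.25 = 4.4 |
| Control only | 0.93 to 1.19 | 1.38 to 1.49 | 1.1/(6/36) = 6.6 |
| Both arms downwards | 1.87 to 2.37 | about 2.8 to 3.0 | 1.1/(3/36) = 13.2 |

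For scale, the pooled SD is √[(32 × 1.96 + 29 × 4.84)/61] = 1.82. So 0.62 points is about a third of an SD, and 0.93 about half. At d = 0.62 the difference is 1.1 − 0.155 = 0.945, a fall of 14%.

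**4. Does the form of GEE matter?** A large-sample simulation used three visits, normal scores with the printed month-6 means and SDs, and dropout of 1/12 and 1/6 before month 6. The earlier-visit means, the correlation between visits, and the strength of dependence of dropout on the month-3 score (log-odds of 1 per SD) are assumptions. The true month-6 difference is 1.10.

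| Assumed correlation | Independence GEE (equals completers' means) | Correct exchangeable GEE, all available visits |
|---|---|---|
| 0.4 | 1.01 | 1.10 |
| 0.6 | 0.97 | 1.09 |
| 0.8 | 0.93 | 1.10 |

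Under these assumptions the first form understates the difference by about 8% to 16%, and the second is nearly unbiased.

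**The case against.** Three arguments carry weight.

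- **The imbalance is weak evidence.** A split of 6 v 3 is well within chance, and unequal dropout alone does not bias a model that contains group. This stands. A reader might infer from the doubled rate that bias occurred, and the documents do not show that. Equally, dropout related to scores can bias a comparison without any clear imbalance.
- **GEE need not fail.** A reader might infer that a GEE is unbiased only if dropout is unrelated to earlier scores. That is too strong: with all available visits and a correct working correlation, the simulated bias is close to nil. But the documents state neither condition, and the population entry points away from the first.
- **The tipping point is not for the planned contrast.** It concerns a simple difference in assumed month-6 means, because the group-by-time estimate cannot be rebuilt from the form. The smallest figure, 0.62, needs a Welch test, completer counts and opposite shifts in the two arms. A reader might infer that a shift of about 0.6 points would remove the adherence result. It would only bring the interval to zero in that most fragile case, leaving 86% of the difference.

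It can also be said that the printed 36 and 36 mean nothing was missing. That conflicts with the flow table and with the stated population, so it cannot be relied on.

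**Conclusion.** The concern holds as a gap in the analysis that leaves a risk of bias; it is not a demonstration of bias. Nine of 72 participants did not complete, and the documents neither protect the comparison against score-related dropout nor test how sensitive it is.

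On the assumptions above, nominal significance could be lost at about 0.6 to 0.8 points (opposite shifts) or 0.9 to 1.2 points (control only). With standard errors from 36/36 these become 0.92 to 0.99 and 1.38 to 1.49. The effect itself would vanish only at 4.4 to 6.6 points under those two patterns. If the entered p of 0.05 really is the calculated value, the result already sits at the threshold and there is no margin. The documents give no mediator results, so no size can be put on the risk there.

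**What to change.** 1. Replace the population defined by 24-week follow-up with all 72 randomised, using every available visit. This step is essential: a different model fitted to the same completers would change little.
2. Analyse adherence and each mediator with a method valid when dropout depends on observed scores. Use either a likelihood-based mixed model for repeated measures, or the same GEE after multiple imputation by arm from baseline and any month-3 scores.
3. Add one delta-adjusted sensitivity analysis that shifts the month-6 scores imputed for those who left, and report the shift at which the conclusion changes.
4. While doing so, reconcile the printed 36/36 with the 33/30 completers, the two missing control reasons, and the entered p of 0.05 and estimate of 0.5.

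The cost is a little analysis work, with no new patients or data. Baseline questionnaires preceded randomisation, so baseline scores should exist for all 72; month-3 scores for those who left may or may not exist. The named package fits linear mixed models, while multiple imputation may need an add-on module or other software. The interval may widen slightly.

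### The GEE has no baseline-score covariate, so a valid treatment contrast is probably less precise than the collected data allow

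*Combined protocol and SAP*

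**What the plan says.** The DATA ANALYSIS paragraph of the Study Protocol names the method only: "The generalized estimating equations were used to analyze the efficacy of the intervention". The model terms appear once, in the Other Statistical Analysis row of the Statistical Analysis Template, where the GEE is used to "model each outcome variable as a function of group effect, time effect, and group by time interaction effect". No covariate, working correlation or list of response visits is given there or elsewhere. ANCOVA appears only as an unselected entry in the template's pick-list.

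The one stated analytic use of baseline data is a comparison of the arms: "Independent t-tests and one-way analysis of variance (ANOVA) were performed to analyze the baseline equivalent between study groups".

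On timing, METHODS says participants were randomised "after completion of baseline questionnaires", and "Data were collected at baseline, third month, and sixth month in both groups". It also says "Allocation was balanced by site by using a minimization method".

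For adherence, a baseline score is implied rather than stated. DATA ANALYSIS lists "adherence to anticoagulant therapies in patients treated with oral anticoagulants for atrial fibrillation" among the GEE outcomes, and the Outcome Measure Template describes the analysed set as "All participants with baseline and at least fellow up for 24 weeks". The instrument list in METHODS, however, does not name the adherence scale.

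**The concern.** The three model terms leave two readings.

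- **A.** Baseline is a level of time. The group-by-time coefficient is then the difference between arms in mean change from baseline, which fixes the slope on baseline at 1.
- **B.** Only months 3 and 6 are responses. The baseline score is then not used, which fixes the slope at 0.

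Conditioning on the baseline score estimates that slope from the data and is generally more precise than either. It is legitimate here because the questionnaires were completed before allocation, so the score cannot be affected by treatment.

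The trial is small: 72 randomised, with 33 and 30 completing according to the Participant Flow Template. The same model serves every outcome. Any lost precision therefore affects the whole efficacy analysis, and recovering it needs no extra patient or visit.

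**Working it through.** The documents give no power or sample-size calculation, so there is no figure of the plan's own to reproduce. The check compares the variance of the month-6 contrast under each reading with its variance after conditioning on baseline.

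**Inputs from the documents.** Completers n1 = 33 (intervention) and n0 = 30 (control), from the Participant Flow Template. Dispersions 1.4 and 2.2 beside the adherence means 8.1 and 9.2, from the Outcome Measure Template.

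**Assumptions.** The dispersions are follow-up SDs (the selected type is not legible). The baseline SD, sb, is the same in both arms: 1.4, 1.8 or 2.2. The baseline-to-follow-up correlation, ρ, is the same in both arms: 0.3, 0.5 or 0.7.

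**Formulas.** Sums run over arms, with s the arm's follow-up SD and n its size.

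- Change (A): Σ (s² + sb² − 2ρ·s·sb)/n
- Follow-up only (B): Σ s²/n
- Adjusted: Σ (s² + b²·sb² − 2b·ρ·s·sb)/n, with pooled slope b = ρ(1.4×32 + 2.2×29)/(61·sb)

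**Worked cell, sb = 1.8 and ρ = 0.5.**

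- b = 0.5 × 108.6/109.8 = 0.495
- Change: 2.68/33 + 4.12/30 = 0.2185
- Follow-up only: 1.96/33 + 4.84/30 = 0.2207
- Adjusted: 1.506/33 + 3.674/30 = 0.1681
- Ratios: 0.1681/0.2185 = 0.77 against change; 0.1681/0.2207 = 0.76 against follow-up only

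**Whole grid.** Each entry is the adjusted variance divided by the planned variance. The simulated values (20,000 runs per cell) include the cost of estimating the baseline and site terms.

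| Planned contrast | sb | Closed form, ρ = 0.3 / 0.5 / 0.7 | Simulated, ρ = 0.3 / 0.5 / 0.7 |
|---|---|---|---|
| A, change | 1.4 | 0.81 / 0.92 / 0.99 | 0.82 / 0.93 / 1.01 |
| A, change | 1.8 | 0.67 / 0.77 / 0.87 | 0.68 / 0.78 / 0.89 |
| A, change | 2.2 | 0.54 / 0.61 / 0.68 | 0.55 / 0.63 / 0.70 |
| B, follow-up only | any | 0.91 / 0.76 / 0.53 | 0.93 / 0.78 / 0.54 |

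A second simulation of the full grid agreed with these values to within about 0.01.

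**On the standard-error scale.** Under A the largest gain is 1 − √0.55 = 26%, and the smallest is nil (ratio 1.01). Under B the range is 1 − √0.93 = 4% to 1 − √0.54 = 27%.

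**Full GEE fits (6,000 runs per cell, nine cells).** The two-visit model with baseline, baseline-by-time and site had variance 0.56 to 1.01 times that of the three-visit model, and 0.54 to 0.94 times that of follow-up only. The alternative is to keep baseline as a response with the arms constrained to a common baseline mean. With an independence working correlation, its ratio to follow-up only was 1.00 in all nine cells, so baseline adds nothing there. Against change, its ratio was 0.56 to 1.06 with an exchangeable and 0.56 to 1.01 with an unstructured working correlation.

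**Validity.** With 36 per arm, no missing data, no true effect and an exchangeable GEE (400 trials per ρ), the group-by-time coefficient equalled the difference in mean change to machine precision. It averaged 0.003 to 0.020, against an empirical SE of 0.34 to 0.54. Rejection at nominal 5% was 5.0% to 7.0%, compared with 5.8% to 7.0% with the covariate.

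**The case against.** The strongest reply is that nothing here is an error. Group, time and group-by-time is a standard repeated-measures model, the contrast is valid, and no stated power target is missed. Baseline is listed as one of three collection times, so reading A is likelier and each patient's baseline already enters by differencing. The gain then depends wholly on quantities the documents omit. The 26% needs a baseline SD of 2.2 in both arms with a correlation of only 0.3. The middle cell gives about 12% (1 − √0.78), and one cell gives nothing. Outside the grid there can be a small loss: about 3 to 4% more variance under B at correlations of 0.1 and 0, and about 2% more under A at SD 1.4 and correlation 0.8. The source is also a single sentence in a results form, and the results are already in.

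Much of this stands. Reading A deserves the greater weight, the gain may be nil, and an adjusted analysis can now only be post hoc. These points limit how much depends on the change. They do not show the planned contrast to be as efficient: eight of the nine cells under A, and all under B, favour adjustment. Brevity explains the silence on responses and working correlation, but the contrast remains unidentified.

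**Conclusion.** The concern holds as a matter of precision. The stated model omits a pre-randomisation covariate that the trial appears to have collected for each outcome. Under the working assumptions, adjustment usually reduces the variance, by up to roughly half, and at worst adds about 1% within the grid. Confidence in the size is moderate, because the correlation, the baseline SD and the reading of 1.4 and 2.2 as follow-up SDs are all assumptions.

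The statement that the planned contrast is valid rests on randomisation with complete data. Nine of 72 did not complete, yet 36 and 36 are reported as analysed; that is a separate question, which baseline adjustment does not settle. The change is worth making, but the existing contrast is not invalid without it.

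**What to change.** 1. State which visits are GEE responses and which working correlation was used.
2. Fit the GEE to the month-3 and month-6 scores with group, time, group-by-time, baseline score, baseline-by-time and site. Do not enter baseline as a covariate while it also remains a response. Site belongs in the model because it is the minimisation factor; it is not there to sharpen the group-by-time estimate.
3. If baseline is kept as a response with equal arm means at baseline, specify a working correlation other than independence.
4. Confirm that the adherence scale was administered at baseline, and add it to the instrument list.
5. Label the adjusted analysis post hoc and present it beside the one already entered.

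The cost is one changed model statement and a few degrees of freedom. No further patients or visits are needed.
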